## LIST OF IN-TEXT FIGURES

#### **FIGURES**

# **PROTOCOL AMENDMENTS**

# **SUMMARY OF CHANGES**

Protocol VersionIssue DateOriginal Protocol27-Sep-2016Amendment 120-Oct-2022

Amendments below are listed beginning with the most recent amendment. Amendment -1 (20-Oct-2022)

Protocol Section	Description of Change						
SYNOPSIS	Added description regarding referring to attachment 3 for dose modification guidelines "Refer to the locally approved prescribing information for Imbruvica TM and Attachment 3 regarding the updated dose modification guidelines, special warnings, precautions for use, and other important information."						
1.2 Overall Rationale for study	Added description regarding referring to attachment 3 for dose modification guidelines "For atrial fibrillation which persists, consider the risks and benefits of ibrutinib treatment and follow the dose modification guidelines as per Attachment 3 in conjunction with local prescribing information"						
6.0 Dosage and Administration	Added description regarding referring to attachment 3 for dose modification guidelines "Refer to the locally approved prescribing information for Imbruvica TM and Attachment 3 regarding the updated dose modification guidelines, special warnings, precautions for use, and other important information."						
Attachments	Added attachment 3						
Investigator Agreement (Last Page)	Change in Sponsor's Responsible Medical Officer: PPD to						

4

#### **SYNOPSIS**

#### **Protocol Title**

A prospective, multicenter, open label single arm Phase IV clinical trial to assess safety of ImbruvicaTM (Ibrutinib capsules 140 mg) in Indian patients with chronic lymphocytic leukemia or mantle cell lymphoma who have received at least one prior therapy or chronic lymphocytic leukemia with 17p deletion

**Sponsor's Responsible Medical Officer:** PPD , Medical Advisor, Johnson & Johnson Private Limited, India.

The term "sponsor" used throughout this document refers to the entities listed in the Contact Information page(s), which will be provided separately.

#### BACKGROUND AND RATIONALE

Ibrutinib is a first-in-class potent, orally-administered, covalently-binding small molecule inhibitor of Bruton's tyrosine kinase (BTK) currently approved by the United States (US) FDA for the treatment of adult patients with mantle cell lymphoma (MCL) who have received at least one prior therapy; for the treatment of patients with chronic lymphocytic leukemia (CLL) who have received at least one prior therapy; and for the treatment of patients with CLL with 17p deletion. Drug Controller General (India) first approved ibrutinib for the treatment of patients with CLL or MCL who have received at least one prior therapy or CLL with 17p deletion in October 2015.

Post-marketing study is useful in identifying new safety issues and trends, which were not observed in previously conducted clinical studies. The data obtained from the present study will help to understand the safety profile of ibrutinib in a real-world Indian scenario compared with that obtained in a controlled clinical environment.

#### **OBJECTIVES**

The aim of the present phase IV clinical trial is to assess the safety of ibrutinib in a routine clinical set-up in Indian patients to address the regulatory requirement.

#### **Objective**

## **Primary Objective**

The primary objective of this study is to evaluate the post-marketing safety of ImbruvicaTM (ibrutinib capsule 140 mg) under actual conditions of use, and to understand the following:

• Incidence of adverse events (AEs) (Serious and Non-serious AEs);

## **Exploratory Objective(s)**

To analyse the following outcomes with ibrutinib:

- Baseline patient and disease characteristics
- Response assessment and progression
- Change in patient reported outcomes as measured by
  - o Quality of Life by EORTC QLQ C-30 instrument (European Organization for Research and Treatment of Cancer Quality of Life Questionnaires Core 30)
  - Fatigue by FACIT Fatigue instrument (Functional Assessment of Chronic Illness Therapy Fatigue)

#### PHASE IV CLINICAL STUDY DESIGN

This is a prospective open label, single arm, multicentre, phase IV interventional study to describe the safety of ImbruvicaTM in Indian subjects. Approximately, 75 subjects, selected by investigators and determined to be eligible for ibrutinib treatment as per protocol eligibility criteria will be enrolled into the study, after written informed consent is obtained. Subjects will be monitored for AEs during treatment of ImbruvicaTM. Participating investigators will be trained on the locally approved prescribing information of ImbruvicaTM by the sponsor designee before the enrolment of first patient

The decision of subjects to participate in this study must not, in any way, impact upon the standard of care that they are receiving or any benefits to which they are otherwise entitled. Prior to data collection, all subjects must sign an informed consent form (ICF) allowing data collection and source data verification in accordance with local requirements and/or sponsor policy. Sponsor shall provide reimbursement for the investigations haematological profile and coagulation profile to monitor the safety as per protocol throughout the study period. Commercial stocks of Ibrutinib affixed with additional investigational labels ( to meet local regulatory requirements) will be provided free of cost by the sponsor to clinical trial subject from the existing distribution channel as per the mentioned duration in the study protocol.

## Screening cum Enrolment Visit (Day 1):

Data collected at this visit may include but not limited to demographics, medical history, disease related history, concomitant medications, patient-reported outcomes (PROs), laboratory investigations (hematological and coagulation profile) etc. The use of ImbruvicaTM is expected to follow the locally approved prescribing information.

Treatment Period: Subjects will be observed for up to 12 months from the treatment initiation. During the study period, data will be collected at monthly intervals for the first 6 months, (monthly visit ± 7 days; Visit 1 to 6). Subsequent visit would be at 9 months ± 7 days [Visit 7], Data collected at this visit will include demographics, medical history, disease related history, AEs, disease progression assessment, concomitant medications, patient-reported outcomes (PROs), laboratory investigations (haematological and coagulation profile) as listed in the TIME AND EVENTS SCHEDULE. The End-of-Treatment (EOT) visit will be conducted after the completion of 12-months ImbruvicaTM treatment (at Visit 8) or on the day at which the patient discontinued the ImbruvicaTM treatment or study. The rationale for such schedule is that in the RESONATE Trial, on long term follow up it was found that the prevalence rates for infection, diarrhoea, and bleeding events were highest for the first 6 months and gradually declined thereafter. Subjects will have post-trial access to ImbruvicaTM for at least one year or as decided by EC whichever is more as per the recommendations of Subject Expert Committee (Oncology & Haematology) made in its 70th meeting held on 23rd May 2018 at Central Drugs Standard Control Organization HQ, New Delhi communicated vide F.N. 12-10/2017-DC (Pt-Johnson-snd).

Follow up period (End of Study Visit): A telephonic follow-up will be conducted 30 days after the EOT Visit.

The observation period including the Enrolment Visit and telephonic follow-up will be up to a maximum duration of 13 months for each patient. The subjects can continue with their prescribed ImbruvicaTM treatment after the end of treatment in consultation with the participating physician. The overall duration of the study, including recruitment [and/or follow up], is expected to be 36 months.

The expected frequency and timing of data collection in this phase IV clinical trial are summarized in the **Error! Reference source not found. Error! Reference source not found.** presented after the synopsis.

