#### DATA SOURCES AND COLLECTION METHODS

The primary data source for this phase IV interventional study will be the medical records of each patient. Source documentation should be in subjects' medical records for all data entered into the CRF. Additionally, patient- completed questionnaires requested by the sponsor will be recorded and will be considered source data.

At each participating site, the same physician must do assessments for an individual patient through the course of study, if possible. Response assessment and progression criteria will be recorded

Patient-reported outcomes will be measured by 2 questionnaires. The EORTC QLQ-C30 is a general cancer assessment, and the FACIT Fatigue Scale specifically assesses aspects of fatigue. Samples of the PRO scales are provided in Attachments 1, and 2. The PRO questionnaires will be collected at the beginning of the clinic visits prior to any procedures or physician interactions according to the **Error! Reference source n ot found.** 

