## **Observation Visits (Visit 1 to Visit 8)**

The subjects will be followed up at every monthly interval during Visit 1 to Visit 6 for the first 6 months, followed by seventh visit at month 9 and eighth visit at month 12, and as outlined in the TIME AND EVENTS SCHEDULE The below mentioned procedure and measurements will be performed

- Current medical history (symptoms & signs if any, physical examination including vitals)
- Disease progression assessment
- Compliance Assessment
- Patient-completed PRO instruments (questionnaires and scales)
  - o FACIT Fatigue Instrument
  - o EORTC QLQ-30
- Type, dosage and duration of concomitant medication
- AEs for ImbruvicaTM (see Section
- Investigations (Hematology and coagulation profile); as per TIME AND EVENTS SCHEDULE.

**Note:** Visit 8 or discontinuation visit will be the EOT Visit.

A discontinuation visit is the visit at which the participating physician is discontinuing ImbruvicaTM or first routine clinic visit after the patient stopped taking ImbruvicaTM on his own.

At the discontinuation visit, information on date and reason(s) for ImbruvicaTM discontinuation will be collected, if available. The data for discontinuation visit will be collected on the EOT Visit page in CRF.

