## 12.1. Definitions

#### 12.1.1. Adverse Event Definitions and Classifications

#### **Adverse Event**

An adverse event is any untoward medical occurrence in a clinical study subject administered a medicinal (investigational or non-investigational) product. An adverse event does not necessarily have a causal relationship with the treatment. An adverse event can therefore be any unfavorable and unintended sign (including an abnormal finding), symptom, or disease temporally associated with the use of a medicinal (investigational or non-investigational) product, whether or not related to that medicinal (investigational or non-investigational) product. (Definition per International Conference on Harmonisation [ICH])

This includes any occurrence that is new in onset or aggravated in severity or frequency from the baseline condition, or abnormal results of diagnostic procedures, including laboratory test abnormalities.

Note: The sponsor collects adverse events starting with the signing of the ICF (refer to Section 12.3.1. All Adverse Events, for time of last adverse event recording).

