### **Attachment 3: Dose Modifications for Adverse Reactions**

ImbruvicaTM therapy should be withheld for any new onset or worsening Grade 2 cardiac failure, Grade  $\geq$  3 non hematological toxicities, Grade 3 or greater neutropenia with infection or fever, or Grade 4 hematological toxicities.

Once the symptoms of the toxicity have resolved to Grade 1 or baseline (recovery), resume IMBRUVICA therapy at the recommended dose as per the tables below.

Table 1: Recommended dose modifications for events of cardiac failure or cardiac arrhythmias:

Events	Toxicity occurrence	MCL/MZL dose modification after recovery Starting Dose 560 mg/day	CLL/SLL/WM/cGVHD dose modification after recovery Starting Dose 420 mg/day
	First	Restart at 420 mg daily	Restart at 280 mg daily
Grade 2 cardiac failure	Second	Restart at 280 mg daily	Restart at 140 mg daily
	Third	Discontinue Imbruvica™	
Grade 3 cardiac	First	Restart at 420 mg daily †	Restart at 280 mg daily †
arrhythmias	Second	Discontinue Imbruvica™	
Grade 3 or 4 cardiac failure Grade 4 cardiac arrhythmias	First	Discontinue Imbruvica™	

<sup>† Evaluate the benefit-risk before resuming treatment.

Table 2: Recommended dose modifications for non-cardiac events:

Events	Toxicity occurrence	MCL/MZL dose modification after recovery Starting Dose 560 mg/day	CLL/SLL/WM/cGVHD dose modification after recovery Starting Dose 420 mg/day
Grade 3 or 4 non-hematological toxicities	First*	Restart at 560 mg daily	Restart at 420 mg daily
	Second	Restart at 420 mg daily	Restart at 280 mg daily
Grade 3 or 4 neutropenia with	Third	Restart at 280 mg daily	Restart at 140 mg daily
infection or fever  Grade 4 hematological toxicities	Fourth	Discontinue Imbruvica™	

\*When resuming treatment, restart at the same or lower dose based on benefit-risk evaluation. If the toxicity reoccurs, reduce daily dose by 140 mg.

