#### 6.1. Adverse Events

The verbatim terms used in the case report form (CRF) by investigators to identify adverse events will be coded using the Medical Dictionary for Regulatory Activities (MedDRA). Any AE occurring at or after the initial administration of study agent through the day of last dose is considered to be treatment emergent. If the event occurs on the day of the initial administration of study agent, and either event time or time of administration are missing, then the event will be assumed to be treatment emergent. If the event date is recorded as partial or completely missing, then the event will be considered to be treatment emergent unless it is known to be prior to the first administration of study agent based on partial onset date or resolution date. All reported treatment-emergent adverse events will be included in the analysis.

For each adverse event, the percentage of subjects who experience at least 1 occurrence of the given event will be summarized by treatment group.

Summary tables will be provided for:

- Overall summary of TEAEs
- TEAEs by SOC and PT

- TEAEs by SOC, PT, and severity (Mild, Moderate and Severe)
- TEAEs by SOC, PT, and NCI-CTCAE toxicity grade (for non-hematological AEs (using NCI-CTCAE Version 4)) TEAEs by SOC, PT, and IWCLL toxicity grade (for hematologic AEs (using IWCLL 2008 criteria))
- TEAEs by SOC, PT, and relationship to study agent (Not Related, Doubtful, Possible, Probable, Very Likely or Related [possible, probably, Very Likely] and Non-related)
- Serious TEAEs by SOC and PT
- Treatment related TEAEs by SOC, PT, and toxicity grade >= 3
- Treatment related serious TEAEs by SOC and PT
- TEAEs leading to discontinuation of study agent by SOC and PT
- AEs leading to death by SOC and PT

In addition to the summary tables, listings will be provided for subjects who had:

- Any TEAEs
- Serious TEAEs (SAEs)
- Severe TEAEs
- Treatment related TEAEs
- TEAEs leading to discontinuation of study agent
- AEs leading to Death

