## 6.2. Clinical Laboratory Tests

The following summary tables will be presented by type of laboratory test:

- Descriptive statistics will be calculated for each laboratory analyte (Hematology and Coagulation) for observed values at each scheduled time point.
- Parameters with predefined National Cancer Institute Common Terminology Criteria for Adverse Events (NCI-CTCAE, Version 4) toxicity grades at each scheduled time point of measurement
- The number and percentage of subjects with NCI-CTCAE grade >= 3 (markedly abnormal) for the parameters with predefined NCI-CTCAE toxicity grades at each scheduled time point of measurement
- Subjects with abnormal laboratory values at all measured time point.
- Subjects with any markedly abnormal laboratory results
- Normal reference ranges.

Since there is no conventional baseline visit, the values and abnormalities will be summarized by visit without change from baseline analysis. But the sensitivity analysis will be performed with baseline defined as Visit 1.

- Descriptive statistics will be calculated for each laboratory analyte (Hematology and Coagulation) at baseline and for observed values and changes from baseline at each scheduled time point.
- Shift tables (cross-tabulations) summarizing the shift in laboratory values from baseline to the worst post baseline measurement experienced by the subject during the study with respect to NCI-CTCAE toxicity grades
- Shift tables (cross-tabulations) summarizing the shift in laboratory values for non-graded parameters from baseline to each scheduled time point of measurement with respect to abnormality criteria (low, normal, high).
- For all participants, a listing to support the sensitivity analysis table will be provided which will include clinical laboratory test results and change from baseline at all measured time points.

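### No pre-dose blood count is captured and the SAP sets treatment-emergence by date alone, so a cytopenia that predates ibrutinib can be counted as a TEAE

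*Protocol*

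**What the plan says.** **Enrolment laboratory work.** The synopsis describes the Day 1 visit in permissive terms: "Data collected at this visit may include but not limited to demographics, medical history, disease related history", and the list goes on to "laboratory investigations (hematological and coagulation profile) etc". Protocol Section 3.1 and SAP 1.2 repeat this with laboratory investigations of no stated type. Section 5 of the protocol, which lists what is to be done at enrolment, has no laboratory item. Its list for Visits 1 to 8 is the first to have one: "Investigations (Hematology and coagulation profile); as per TIME AND EVENTS SCHEDULE". The Time and Events Schedule appears to leave the enrolment column blank for both panels, although that table did not extract cleanly.

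**What the SAP found.** The SAP amendment history (version 2.0) gives the absence of laboratory data before dosing as the reason for changing Section 6.2. That section begins the change with "Since there is no conventional baseline visit". It drops change from baseline from the main laboratory tables and adds a sensitivity analysis with Visit 1 as baseline. Protocol 11.4 still plans every analyte at baseline, with changes from it.

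**How adverse events are classified.** Protocol 12.1.1 includes laboratory abnormalities among adverse events and covers what is "new in onset or aggravated in severity or frequency from the baseline condition". Protocol 11.4 defines treatment-emergence by onset on treatment or by worsening since baseline. SAP 6.1 uses timing only: "Any AE occurring at or after the initial administration of study agent through the day of last dose is considered to be treatment emergent". An event with a partial or missing date is treated as emergent unless it is known to precede the first dose. The SAP's primary endpoint is the number and type of TEAEs; the protocol's is the number and type of all AEs.

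**The concern.** Version 2.0 of the SAP adapted the laboratory tables to the missing baseline but left the adverse event rule in Section 6.1 unchanged. Subjects are mostly previously treated for CLL or MCL, so some may start ibrutinib with low counts caused by disease or earlier therapy. If the study's first count is taken on drug, nothing in the study database shows whether a low value is new, worse or unchanged.

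The protocol's own safety overview names neutropenia, thrombocytopenia and anaemia as the most common haematological Grade 3 or 4 events, so the affected category is an important one. The study has a single arm, so no comparator group would show the same misclassification and let a reader allow for it. Both endpoint versions are exposed: the SAP's through the date rule, and the protocol's because its definition of an adverse event itself depends on the baseline condition.

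**Working it through.** **1. The plan's own figure.** The only figure is N = 75, taken from a committee recommendation. No rate, precision target or power stands behind it, so there is no calculation to reproduce.

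**2. Timing of the first study count.** Visit 1 is a monthly visit with a window of 7 days either side. With Day 30 as target (the Visit 1 target day in SAP Table 1A, which is set for the PRO analysis), the window is 30 - 7 = Day 23 to 30 + 7 = Day 37. The first scheduled count is therefore taken after about three to five weeks on drug.

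**3. Path to misclassification.** All of the following must happen:

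- a cytopenia exists before the first dose;
- no pre-dose value reaches the study data (as the SAP reports);
- the count is low at Visit 1;
- the investigator judges it a clinically relevant change and records it as an AE;
- the onset is entered as the Visit 1 date, or is left partial or unknown.

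Under SAP 6.1 the event is then a TEAE. The sensitivity baseline in SAP 6.2 does not help: Visit 1 is itself an on-drug value, and that analysis does not feed into Section 6.1.

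**4. Illustrative size.** The documents give no prevalence of cytopenia before treatment, so every input except N is an assumption:

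- p = true incidence of on-drug cytopenia AEs, 20%;
- q = prevalence of cytopenia before the first dose, 10% to 30%;
- r = probability that an old cytopenia is recorded as a new AE, 25% to 50%.

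Taking old and new cytopenia as independent, observed incidence = p + (1 - p) × q × r, and extra subjects = 75 × (1 - p) × q × r.

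| q | r | Extra incidence | Observed incidence | Extra subjects of 75 |
|---|---|---|---|---|
| 10% | 25% | 0.80 × 0.10 × 0.25 = 2 points | 22% | 1.5 |
| 20% | 50% | 0.80 × 0.20 × 0.50 = 8 points | 28% | 6 |
| 30% | 50% | 0.80 × 0.30 × 0.50 = 12 points | 32% | 9 |
| any | 0% | 0 points | 20% | 0 |

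The shorter product 75 × q × r would give 75 × 0.10 × 0.25 = 1.9 to 75 × 0.30 × 0.50 = 11.3. It overstates the effect because it counts subjects who would have had an on-drug cytopenia TEAE anyway.

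**5. Against sampling error.** At a true 20% (15 of 75) the exact 95% interval is 11.6% to 30.8%, which reaches 30.8 - 20 = 10.8 points above the estimate. The low end of the illustration (2 points) is well inside that; the high end (12 points) is slightly beyond it.

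**6. Dependence on the assumptions.** Over p = 10-30%, q = 10-40% and r = 25-100%, the extra subjects run from 75 × 0.70 × 0.10 × 0.25 = 1.3 to 75 × 0.90 × 0.40 × 1.00 = 27. The documents do not narrow this range.

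**The case against.** A reader might infer that pre-existing cytopenias will be counted as TEAEs. The documents do not support that, because several safeguards stand in the way:

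- The AE definition covers only what is new or aggravated, so a stable old cytopenia is not an AE.
- Protocol 9.2 sends only changes that the investigator judges clinically relevant to the AE pages.
- Medical history, disease characteristics and prior therapy are recorded at enrolment.
- The synopsis (Safety Assessment) provides for recording routine laboratory results, and the physician has the chart.
- SAP 6.1 tabulates TEAEs by relationship, and the doubtful category allows for concomitant disease or drugs.

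These points make misclassification a risk rather than a certainty, but they do not close the gap. Judging a change needs an earlier value. The medical history item asks for no count, grade or date. Routine results are recorded only where they happen to exist, without clear cover for the time before consent, and the SAP reports that no pre-dose laboratory data were captured. The relationship tables do not alter the TEAE count.

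A reader might also infer that the protocol requires laboratory tests at enrolment and then omits them. The enrolment wording is permissive, so this is loose drafting and not two conflicting requirements. Nor do the documents support saying that the results cannot be compared with earlier trials, since they do not describe how those trials handled laboratory baseline. Finally, Attachment 3's reference to baseline can be read as addressed to a clinician with the chart. It does not say that a study-recorded value is needed, so that reference calls only for reconciliation.

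**Conclusion.** The concern stands as a gap in the primary safety analysis. No laboratory values were captured before dosing, and SAP 6.1 has no rule for a cytopenia AE that lacks a pre-dose count. Haematological TEAE incidence may therefore be biased upward. The amount cannot be determined from the documents. It is zero if investigators recognise every old cytopenia, and about 1.5 to 9 of 75 subjects (2 to 12 points) under the assumptions p = 20%, q = 10-30%, r = 25-50% and independence. The sponsor should correct this: it bears on the primary endpoint of a single-arm study and can be repaired cheaply from records.

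**What to change.** 1. **Reconcile the passages.** Bring the enrolment text in the synopsis and Section 3.1, and the baseline laboratory analyses in protocol 11.4, into line with the Section 5 visit lists, the Time and Events Schedule and SAP 6.2. Reconcile the reference to baseline in Attachment 3 with whatever is collected. No clinical rule is proposed here.
2. **Use the medical record.** The synopsis already says: "The primary data source for this phase IV interventional study will be the medical records of each patient". Extend its provision for routine results to the last blood count and clotting result before the first dose, with the date, and use these to judge whether a cytopenia is new or aggravated. Section 5 already has a similar look-back of 12 weeks at the telephone follow-up.
3. **Add a rule to SAP 6.1.** Flag haematological TEAEs first detected at or before Visit 1 in subjects with no pre-dose value. Report incidence with and without them, as a range. State that the figure without them also removes genuine early drug effects, so it is not a corrected estimate.

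Cost: chart look-up and data entry for up to 75 subjects, one set of CRF fields and two SAP sentences. No new blood draw is needed. The main limitation, to be stated in the report, is that routine values will differ in date and laboratory, and some subjects may have none.
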